#### 14. STUDY MEDICATION COMPLIANCE

Compliance with study medication—based on the drug exposure data—will be calculated as the amount taken divided by the prescribed amount expressed as a percentage. "Per Visit" Compliance to GX-188E, Overall Compliance to GX-188E, "Per Visit" Compliance to Pembrolizumab and Overall Compliance to Pembrolizumab will be calculated.

The compliance will also be summarized by categories as below:

- < 80%
- 80 120%
- > 120%

The variables relevant to compliance to study medication will be presented in summary table for the safety population. Individual data will be listed.

#### 14.1. DERIVATIONS

"Per Visit" Compliance to GX-188E (%) = (Dose in mg administrated at location 1+Dose
in mg administrated at location 2)/Planned dose in mg per day\*100, presented to 1
decimal place.

Planned dose per day is total of 2 mg per vaccination day.

• Overall Compliance to GX-188E (%) = Actual Number of Doses of GX-188E / Planned Number of Doses of GX-188E Injection

Planned number of doses of GX-188E (times) = 6

- "Per Visit" Compliance to Pembrolizumab (%) =Dose in mg per administration /Planned dose in mg per administration \*100, presented to 1 decimal place.
- Overall Compliance to Pembrolizumab (%) = Actual Number of Doses of Pembrolizumab
   / Planned number of doses of Pembrolizumab

Planned number of doses of Pembrolizumab (times) = 35

Document: \\ieedc-vnac01\Biosdata\Genexine\GX-188E\GYA02599\Biostatistics\Documentation\SAP

Author: [name] Version Number: 1.1

Version Date: 05Sep2022

PROTOCOL GX-188E-005

Template No: CS\_TP\_BS016 Revision 6 Reference: CS\_WI\_BS005

PROTOCOL GX-188E-005

Analysis Plan Page 27 of 48

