#### 12.1.2.1 **Reduction Level 1 GX-188E**

The modification to GX-188E administration at Reduction Level 1 involves removal of the GX-188E vaccination at Week 2 Day 1. At Reduction Level 1, GX-188E will be administered Week 1 Day 1, Week 4 Day 1, Week 7 Day 1, Week 13 Day 1, Week 19 Day 1 and Week 46 Day 1(Optional).

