#### Part A. Initial Safety Evaluation

The study will begin with Part A, a safety run-in, employing a "6+3 design", to ensure that the study treatment is not associated with unacceptable acute toxicities.

The starting dose in Part A for GX-188E will be 2 mg (1 mg/site x 2 vaccination sites). Six (6) vaccination days are planned. (week 1, week 2, week 4, week 7, week 13 and week 19). An optional GX-188E administration may be given at week 46 if it is in the best interests of the patient, as determined by the investigator, once the patient has completed 37 weeks of treatment. Additional GX-188E administration(s) may be given to the patient after discussion with the sponsor.

GX-188E will be administered on Day 1 of the following schedule:

Weeks 1, 2, 4, 7, 13, 19 and 46 (Optional)

The standard dose of pembrolizumab (200 mg every 3 weeks) will be administered. No dose escalation of either agent is planned.

The first 6 patients will be enrolled and evaluated for the first 3 weeks (prior to week 4 Day 1 visit) for dose-limiting toxicities (DLTs). A DLT is defined as any adverse event (AE) that is not clearly due to progression of the patient's malignancy, that occurs within the first 3 weeks (prior to week 4 Day 1 visit) of treatment initiation, and that meets at least one of the non-hematologic or hematologic criteria.

In addition, any other AE that is felt to be treatment-limiting in the medical opinions of the principal Investigator and the Sponsor's Medical Monitor may be considered a DLT.

No additional patients will be enrolled until all patients in Part A have completed the DLT window and the investigational treatment regimen has been deemed safe. If  $\leq$  1 patient of 6 enrolled patients experiences DLT, enrolment into Part B will be initiated. If 2 patients experience a DLT, an additional 3 patients will be enrolled and evaluated for DLTs. If 3 or more patients in the first 6 or 9 patients experience a DLT, the combination at the current treatment schedule will be considered too acutely toxic and enrolment will begin at a reduced frequency treatment schedule.

Document: \\ieedc-vnac01\Biosdata\Genexine\GX-188E\GYA02599\Biostatistics\Documentation\SAP

Author: [name] Version Number: 1.1

Version Date: 05Sep2022

Template No: CS\_TP\_BS016 Revision 6 Reference: CS\_WI\_BS005

Analysis Plan Page 12 of 48

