#### 13.1. DERIVATIONS

- Duration of exposure to GX-188E (weeks)= (Last dose date of GX-188E First dose date of GX-188E +1) / 7
  - When the start or stop date is missing, then the exposure will be treated as missing. Interruptions, compliance, and dose changes are not taken into account for duration of exposure.
- Number of Doses of GX-188E (times) = Count total numbers from "Exposure GX-188E Vaccination" CRF page with response of "Yes" to the question "Was GX-188E administered at this visit?"
- Duration of exposure to Pembrolizumab (weeks)= (Last dose date of Pembrolizumab First dose date of Pembrolizumab +1) / 7
  - When the start or stop date is missing, then the exposure will be treated as missing. Interruptions, compliance, and dose changes are not taken into account for duration of exposure.
- Number of Doses of Pembrolizumab (times) = Count total numbers from "Exposure Pembrolizumab" CRF page with response of "Yes" to the question "Was Pembrolizumab administered at this visit? "

Document: \\ieedc-vnac01\Biosdata\Genexine\GX-188E\GYA02599\Biostatistics\Documentation\SAP

Author: [name] Version Number: 1.1

Version Date: 05Sep2022

Template No: CS\_TP\_BS016 Revision 6 Reference: CS\_WI\_BS005

Analysis Plan Page 26 of 48

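### Overall GX-188E compliance (SAP 14.1) counts optional doses in the numerator but divides by a fixed 6, so some patients get a wrong percentage and a wrong category

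*SAP*

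**What the plan says.** SAP 14 bases compliance on the drug exposure data and defines it as the "amount taken divided by the prescribed amount", expressed as a percentage. The result is also grouped as <80%, 80-120% and >120%, for the safety population.

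SAP 14.1 gives the overall measure as "Overall Compliance to GX-188E (%) = Actual Number of Doses of GX-188E / Planned Number of Doses of GX-188E Injection", and then sets "Planned number of doses of GX-188E (times) = 6" for every patient.

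SAP 13.1 derives the number of GX-188E doses by counting the exposure pages answered Yes to the question "Was GX-188E administered at this visit". The count is not limited to the scheduled visits.

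SAP 3.1 (Part A) states that "Six (6) vaccination days are planned", at Weeks 1, 2, 4, 7, 13 and 19. It then allows an optional Week 46 dose once 37 weeks of treatment are complete, and adds: "Additional GX-188E administration(s) may be given to the patient after discussion with the sponsor". No upper limit is given.

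Protocol 12.1.2.1 describes a reduced schedule that "involves removal of the GX-188E vaccination at Week 2 Day 1", which leaves five scheduled doses.

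**The concern.** The numerator and the denominator describe different things. The denominator is the scheduled six-dose course. The numerator is every dose given, whether scheduled, optional or added later. This departs from SAP 14's own definition, because an optional dose enters the amount taken without entering the amount prescribed.

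There are two consequences. A patient who missed scheduled vaccinations can have them cancelled out by later optional ones and move into the 80-120% group. A patient who received exactly what the protocol permits can appear above 120%. The distortion is also uneven, because only patients still on treatment at about Week 37 or later can receive the Week 46 dose.

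What is at stake is the accuracy of the overall compliance summary that a reader of the study report would see.

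**Working it through.** **Inputs**
- Scheduled doses: Weeks 1, 2, 4, 7, 13, 19, which is 6 (SAP 3.1). This reproduces the denominator in SAP 14.1.
- Optional dose: one at Week 46. Further doses: number not capped (SAP 3.1).
- Numerator: all visits with GX-188E given (SAP 13.1).
- Categories: <80%, 80-120%, >120% (SAP 14).
- Reduction Level 1: Weeks 1, 4, 7, 13, 19, which is 5 scheduled doses (Protocol 12.1.2.1).

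**Formulas**

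Let k be the doses given at the six scheduled visits and e the optional or additional doses.
- SAP rule: (k + e)/6 × 100
- Scheduled course only: k/6 × 100

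**Results**

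| k | e | SAP rule | Category | Scheduled only | Category | Category changes? |
|---|---|---|---|---|---|---|
| 4 | 1 | 5/6 = 83.3% | 80-120% | 4/6 = 66.7% | <80% | Yes |
| 5 | 1 | 6/6 = 100% | 80-120% | 5/6 = 83.3% | 80-120% | No |
| 6 | 1 | 7/6 = 116.7% | 80-120% | 6/6 = 100% | 80-120% | No |
| 3 | 2 | 5/6 = 83.3% | 80-120% | 3/6 = 50.0% | <80% | Yes |
| 4 | 2 | 6/6 = 100% | 80-120% | 4/6 = 66.7% | <80% | Yes |
| 5 | 2 | 7/6 = 116.7% | 80-120% | 5/6 = 83.3% | 80-120% | No |
| 6 | 2 | 8/6 = 133.3% | >120% | 6/6 = 100% | 80-120% | Yes |

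**General rule**
- The SAP value reaches 80% when k + e ≥ 4.8, that is 5 doses, and exceeds 120% when k + e > 7.2, that is 8 doses.
- A patient therefore moves from <80% to 80-120% only if k ≤ 4 and k + e is 5, 6 or 7. This needs at least two missed scheduled doses.
- A patient lands above 120% only if k + e ≥ 8, which needs at least two extra doses.
- With Week 46 as the only extra dose (e = 1), k = 4 is the only pattern that changes category.

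**Reduction Level 1, if any patient received it (e = 0)**
- All 5 scheduled doses: 5/6 = 83.3% instead of 5/5 = 100%; same category.
- 4 of 5: 4/6 = 66.7% (<80%) instead of 4/5 = 80.0% (80-120%); the category changes.

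**The case against.** **The link between 14.1 and 13.1 is inferred.** SAP 14.1 does not cite 13.1 or mention Week 46, and the table shells, which might settle the matter, are not in the documents. This is true. But SAP 14 ties compliance to the exposure data, 13.1 holds the only GX-188E dose count, and nothing in SAP 13 or 14 excludes optional doses. A programmer following the text would use that count.

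**The reach is narrow.** This stands. A category change from Week 46 alone needs a patient who missed exactly two scheduled vaccinations, completed 37 weeks and was then chosen for the optional dose. The percentage itself, however, is wrong for every patient with an extra dose.

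**Reduction Level 1 is probably moot.** SAP version 1.1 was written after Part B had passed its first stage, so the schedule had already been chosen, and a planned count of 6 fits the starting schedule having been kept. The documents do not say so outright. This part is conditional and carries little weight.

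**k/6 is not pure adherence either.** A patient who received every dose due at Weeks 1, 2, 4 and 7 and stopped at Week 10 for progression shows 4/6 = 66.7%. That limitation stands: k/6 measures completion of the scheduled course and shares this feature with the present rule. It does remove the mismatch between numerator and denominator.

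**Another repair exists.** Adding each extra dose to the denominator, (k + e)/(6 + e), gives 71.4%, 85.7% and 100% for k = 4, 5, 6 with e = 1, and 100% for k = 6 with e = 2. The categories match those from k/6. It still lets extra doses dilute missed ones: k = 4 with e = 4 gives 8/10 = 80.0%, back in the 80-120% group. That favours k/6.

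**The information is available elsewhere.** Per-visit compliance, the dose-count summary and the individual listings let a reader trace missed and extra doses. This limits the harm but does not make the overall figure correct.

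**Conclusion.** The rule in SAP 14.1 is wrong as written, and the point is minor. For any patient with an extra dose the percentage is overstated by e/6, that is 16.7 percentage points per extra dose. The category is wrong only in the patterns set out above: among patients whose only extra dose is Week 46, those with exactly 4 scheduled doses; with two extra doses, those with 3, 4 or 6.

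This assumes that the actual number of doses in 14.1 is the count defined in 13.1. The number of patients affected cannot be derived from the documents.

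The effect stops at one descriptive safety-population table. No efficacy endpoint, analysis population or error rate uses overall compliance.

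**What to change.** In SAP 14.1, define overall GX-188E compliance (%) as the number of doses given at Weeks 1, 2, 4, 7, 13 and 19, divided by 6, times 100. For any patient on Reduction Level 1, use Weeks 1, 4, 7, 13 and 19, divided by 5, times 100. Report receipt of the Week 46 dose (yes/no) and the number of further doses on two separate rows, outside the three compliance categories. Leave the total dose count in SAP 13.1 unchanged for the exposure table.

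The cost is one revised derivation and two extra table rows. Dosing is already recorded by visit, so no new data or procedures are needed.

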### Pembrolizumab will continue to be administered once every 3 weeks.

Blood CEA/TA4 levels and thyroid function tests will be performed approximately every 6 weeks for the duration of study participation.

Research blood will be collected further at Week 22, Week 49, and every 27 weeks thereafter. (Including blood sample for Flt-3L level monitoring). Research blood collections are not performed on Day 1 of Week 103 visit but at the EOS visit.

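### Overall pembrolizumab compliance in SAP 14.1 divides by the 35-dose maximum for every patient, so its categories mainly show time on treatment rather than missed doses

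*SAP*

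**What the plan says.** SAP 14 says that compliance is "calculated as the amount taken divided by the prescribed amount expressed as a percentage". SAP 14.1 then defines overall compliance for each agent as the actual number of doses over a planned number, and sets the planned numbers as constants: "Planned number of doses of Pembrolizumab (times) = 35" and "Planned number of doses of GX-188E (times) = 6". It makes no allowance for discontinuation, for patients still on treatment at the data cut-off, for the reduced GX-188E schedule, or for GX-188E doses beyond the sixth.

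The results are grouped as below 80%, 80 to 120%, and above 120%. On the population SAP 14 states: "The variables relevant to compliance to study medication will be presented in summary table for the safety population". That population includes anyone who received one dose of either agent.

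In the protocol, 35 pembrolizumab treatments is a ceiling. Section 19.1 lists reaching it among the reasons to stop. The synopsis (Duration of Participation) sets a two-year limit that ends sooner if progression is confirmed. Section 22.3 takes patients with confirmed progression off treatment, with an exception possible after consulting the sponsor. Section 19.1 also lets discontinuation be considered after a confirmed complete response once at least 8 cycles have been given. SAP 4.3 ties the final analysis to completion of the 24-week tumor assessments in all 60 patients and accepts that some may still be on treatment then.

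**The concern.** The constant does not match the SAP's own definition. Once a patient stops as the protocol directs, nothing more is prescribed, yet every dose between that stop and the thirty-fifth counts against her. The same applies to doses that fall after the data cut-off for a patient who is still being treated.

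At stake is how one table and its listing are read. Under a compliance heading, the pembrolizumab column can show low percentages in patients who missed nothing, and it cannot separate them from patients who really skipped doses. Per-visit compliance does not fill the gap, because it compares the milligrams given at an administration with the milligrams planned for it. It says nothing about administrations that did not take place.

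**Working it through.** **Inputs**
- Pembrolizumab interval: "Pembrolizumab will continue to be administered once every 3 weeks" (Protocol 16.11). First dose Week 1; last possible dose Week 103 Day 1 (Protocol 16.11.1).
- GX-188E planned days: Weeks 1, 2, 4, 7, 13 and 19, with Week 46 optional and further doses possible after discussion with the sponsor (Protocol synopsis; SAP 3.1).
- Reduced schedule: "The modification to GX-188E administration at Reduction Level 1 involves removal of the GX-188E vaccination at Week 2 Day 1" (Protocol 12.1.2.1), which leaves 5 planned doses.
- Fixed denominators 35 and 6, and cut-offs 80% and 120% (SAP 14 and 14.1).

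**Step 1: reproduce the plan's figures.** Pembrolizumab: (103 − 1)/3 + 1 = 35. GX-188E: six listed weeks = 6. Both constants equal the full course.

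**Step 2: what 80% requires for pembrolizumab.** 0.80 × 35 = 28 doses. On schedule the 28th dose falls at Week 1 + 27 × 3 = Week 82. One dose fewer gives 27/35 = 77.1%.

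**Step 3: a patient who misses no dose, by week of last dose**

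| Last dose | Pembrolizumab doses | Doses/35 | Category |
|---|---|---|---|
| Week 10 | 4 | 11.4% | below 80% |
| Week 19 | 7 | 20.0% | below 80% |
| Week 22 (last dose visit within 24 weeks) | 8 | 22.9% | below 80% |
| Week 46 | 16 | 45.7% | below 80% |
| Week 79 | 27 | 77.1% | below 80% |
| Week 82 | 28 | 80.0% | 80 to 120% |
| Week 103 | 35 | 100% | 80 to 120% |

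A patient with a confirmed complete response who stops after 8 doses also scores 22.9%.

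**Step 4: the top category.** 1.20 × 35 = 42, so above 120% means at least 43 doses. With a ceiling of 35 the ratio cannot exceed 100%.

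**Step 5: GX-188E against the fixed 6**
- Four doses, stopping before Week 13: 4/6 = 66.7%, below 80%.
- Five doses, stopping after Week 13: 5/6 = 83.3%. Six doses: 100%.
- With the optional Week 46 dose: 7/6 = 116.7%, still within 80 to 120%.
- With one further dose: 8/6 = 133.3%, above 120%.
- Complete course on the reduced schedule: 5/6 = 83.3%, within 80 to 120%.

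**Step 6: pembrolizumab with doses scheduled up to the stop as denominator**

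| Stop, before that visit's dose | No dose missed | Same patient under the fixed 35 | One dose missed |
|---|---|---|---|
| Week 10 | 3/3 = 100% | 3/35 = 8.6% | 2/3 = 66.7% |
| Week 19 | 6/6 = 100% | 6/35 = 17.1% | 5/6 = 83.3% |
| Week 28 | 9/9 = 100% | 9/35 = 25.7% | 8/9 = 88.9% |

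The ratio now moves only when a scheduled dose is missed.

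**The case against.** The case for leaving the SAP alone has several parts.

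- **Nothing inferential rests on the ratio.** No analysis population uses it, and ORR24, its exact test and its confidence interval do not change. This stands and keeps the point minor.
- **The denominator is disclosed.** It is openly called a planned number, and SAP 9, 13 and 16.1.3 separately report reasons for withdrawal, duration of exposure, number of doses, interruptions, and adverse events that led to interruption or discontinuation. A careful reader could piece together why a percentage is low. This stands in part. The percentage of patients with an interruption does not say how many doses were missed, and overall compliance is the one planned per-patient percentage that could.
- **GX-188E behaves differently.** Five of the six doses are given by Week 13, so most later stops land within 80 to 120%. A single optional dose does too, and so does a full reduced-schedule course. This stands; the two agents should not be described alike.

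A reader might go further and infer that nearly every patient will be labelled non-compliant with pembrolizumab. The documents do not support that. They give no assumption about time on treatment, so the share of patients with fewer than 28 doses cannot be derived, and the SAP's categories are percentages, with no category called non-compliant. Nor do they show that the reduced schedule was ever used; it opens only if at least 3 patients in 6 or 9 have a dose-limiting toxicity.

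**Conclusion.** The point holds for pembrolizumab. As written, a fully adherent patient whose last dose is before Week 82 falls below 80%, whether she stopped for progression, toxicity or response, or was still on treatment at the cut-off. The top category is empty by construction. The table therefore mainly shows time on treatment. This follows from the fixed 35 and the three-week schedule alone; no progression rate is assumed.

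For GX-188E the defect is smaller. Among fully adherent patients on the six-dose schedule, only those who stop before the Week 13 dose are placed below 80%, and only those given at least two doses beyond the planned six go above 120%. The reduced-schedule figure matters only if that schedule was used.

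The consequence is a misleading descriptive table in the safety population. No efficacy conclusion changes.

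**What to change.** In SAP 14.1, replace both constants by the number of doses scheduled from first dose to treatment discontinuation or data cut-off, whichever is earlier, under the patient's assigned schedule.

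Report optional or additional GX-188E doses separately, outside the ratio. Adding them to both numerator and denominator would hide real misses: a patient who missed one of the six planned doses and received two extra would show 7/8 = 87.5% instead of 5/6 = 83.3%.

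If the present ratio is kept, relabel it as the proportion of maximum planned doses received and do not present it as compliance.

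The cost is a short change to the SAP wording and simple programming before database lock. No new data are needed.

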#### 15. EFFICACY OUTCOMES

Tumor response to treatment will be evaluated using both RECIST v1.1 and iRECIST. For each patient with objectively measurable disease and who meet the criteria for inclusion in the Efficacy Evaluable population, response to therapy will be calculated. The analysis of ORR24, BORR and DCR per RECIST v1.1 will also be performed in safety population as sensitivity analysis.

RECIST 1.1 will be used by BICR as the primary measure for assessment of tumor response, date of disease progression, and as a basis for all protocol guidelines related to disease status (e.g., discontinuation of study treatment). All efficacy endpoints will be evaluated and categorized using RECIST 1.1. Confirmatory scans are required for all determinations of objective response [Partial response (PR) or Complete response (CR)], Stable disease (SD) and disease progression (PD). Confirmatory scans must be performed at least 4 weeks later.

Investigator assessment of tumor response based upon RECIST v1.1 will be analyzed in the same way as the corresponding BICR-assessed endpoints (except Kaplan-Meier curves which will only be presented for BICR assessment). Concordance between BICR and Investigator assessments will be summarized at a patient level for BOR.

iRECIST is based on RECIST 1.1, but adapted to account for the unique tumor response seen with immunotherapeutic drugs. iRECIST will be used by the investigator to assess tumor response and progression and make treatment decisions. When clinically stable, participants should not be discontinued until progression is confirmed by the Investigator, working with local radiology, according to the rules outlined in Appendix 6 of protocol. This allowance to continue treatment despite initial radiologic PD takes into account the observation that some participants can have a transient tumor flare in the first few months after the start of immunotherapy, and then experience subsequent disease response. This data will be captured in the clinical database.

Efficacy endpoints are as follows.

- Objective Response Rate within 24 weeks (ORR24)
- Best Overall Response Rate (BORR)
- Progression-Free Survival including 6-month PFS rate and median PFS time
- Overall Survival including 6-month OS rate and median OS time
- Disease Control Rate
- Duration of Response
- Time to Best Response

Document: \(\)\ieedc-vnac01\\Biosdata\\Genexine\\GX-188E\\GYA02599\\Biostatistics\\Documentation\\SAP\)

Author: [name] Version Number: 1.1

Version Date: 05Sep2022

Template No: CS\_TP\_BS016 Revision 6 Reference: CS\_WI\_BS005

Analysis Plan Page 28 of 48

